11.1 Study Hypotheses

Alternate hypothesis: Patients undergoing BMBA who receive distraction techniques (room décor, music, and virtual reality) will have lower levels of distress and pain than

patients who receive only the standard of practice care. Additionally, these patients will have higher levels of satisfaction with their overall experience.

Null hypothesis: Patients undergoing BMBA who receive distraction techniques will have no change in their level of distress and pain when compared to patients receiving the standard of practice care. Additionally, the satisfaction of these patients will be comparable to the satisfaction of patients receiving the standard of care.

11.2 Analysis Plans

Endpoints: All endpoints are measured pre- and post-procedure.

The primary endpoints are

1. Q13: a scale from 0-10, measuring pre-procedure patient distress, which will be treated as a numeric value in statistical analysis.
2. Q16: a scale from 0-10, measuring post-procedure patient distress, which will be treated as a numeric value in statistical analysis

The secondary endpoints are

1. Q12: a scale from 0-10, measuring patient pain scores, which will be treated as a numeric value in statistical analysis
2. Q17: a scale from 0-10, measuring post-procedure patient pain scores, which will be treated as a numeric value in statistical analysis
3. Q18, which is on a 5-level Likert scale, measuring satisfaction. This endpoint focuses on the post-procedure response and does not have a pre-procedure comparison.

Statistical Analysis: Responses to the questionnaire before and after the procedure will be reported using summary statistics such as means, standard deviations and proportions. The numeric difference between post vs. pre responses of Q13, Q16, Q12 and Q17 will be compared between Intervention 1 and Control in Phase I, and between Intervention 2 and Control in Phase II, using two-sample t-test. The post-responses of Q18 will be compared between the procedures in Phase I and Phase II using two-sided test for ordinal categorical variables.

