Our hypothesis is that patients undergoing bone marrow biopsy and aspiration (BMBA) who receive distraction techniques (room décor, music, and virtual reality) will have lower levels of distress and pain than patients who receive only the standard of practice care. Additionally, these patients will have higher levels of satisfaction with their overall experience. This study aims to evaluate pre-procedure and post-procedure distress and

pain scores, and post-procedure satisfaction ratings to determine if one or both of the selected interventions are valuable to employ in-clinic for the entire patient population.

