2.1.2 Secondary

To assess patient pain scores related to their BMBA procedure. This will be measured through the 0-10 Numeric Pain Intensity Scale

To assess patient satisfaction with their procedure. This will be assessed through a patient satisfaction survey including Likert-type questions.

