2.2.2 Secondary

The secondary endpoint of patients' pain scores during BMBA procedures are the responses to Question 12 and 17 of the post-procedure survey.

The secondary endpoint of patients' satisfaction levels towards their BMBA procedures is the response to Questions 18 of the post-procedure survey.

3 Study Design

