6.3 Treatment Period

Visit 1, Day 1

- Confirm patient is comfortable proceeding with assigned intervention during BMBA procedure.
- Standard of care BMBA procedure.
- Assess post-procedure vital signs: heart rate, blood pressure, respiratory rate.
- Administer post-procedure questionnaire, which includes:
 - Assessment of current distress level (0-10 scale).
 - 0-10 Numeric Pain Intensity scale.
 - Patient satisfaction questions.

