- I practice breathing techniques or meditate
- None of the above, I don't know how to handle my distress
- None of the above, I don't feel distress about bone marrow biopsies.
- Other (*please elaborate*)

End of Block: Distress Assessment

Start of Block: Divider

Thank you for completing this part of the survey. Please return the iPad to the study team member. You will complete the rest of the survey after your procedure.

End of Block: Divider

Start of Block: Post-procedure

Post-procedure Questions

Q16 At the start of your visit, you rated your distress as a \${Q13/ChoiceGroup/SelectedChoices} out of 10.

On a scale of 0 to 10, with 0 being *no distress* and 10 being *extreme distress*, how much **distress** do you feel now?

- 0
- 1
- 2
- 3
- 4
- 5
- 6
- 7
- 8
- 9
- 10

Q17 During your bone marrow biopsy procedure experience, how would you rate your **pain**, on a scale of 0 to 10, with 0 being *no pain* and 10 being *extreme pain*?

0

1

2

3

4

5

6

7

8

9

10

Q18 Please rate your satisfaction with each of the following parts of your bone marrow biopsy experience.

| | Extremely Dissatisfied | Dissatisfied | Neither Satisfied or Dissatisfied | Satisfied | Extremely Satisfied |
|---|------------------------|-----------------------|-----------------------------------|-----------------------|-----------------------|
| Time spent in the procedure room before the biopsy |  |  |  |  |  |
| Interactions with staff |  |  |  |  |  |
| Room decor |  |  |  |  |  |

End of Block: Post-procedure

Start of Block: Intervention Specific Questions

Display This Question:

If Patient enrollment group = Intervention 2

As part of this study, you were provided with a selection of music and changes to your procedure room decor. These will be referred to as an "**intervention**" in the following questions. Please answer the following questions about your experience as it relates to this intervention.

Display This Question:

If Patient enrollment group = Intervention 1

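### No control patient gives an overall satisfaction rating, so the hypothesis of higher overall satisfaction cannot be tested directly; how the three Q18 ratings are analysed is also left open

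*Combined protocol and SAP*

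**What the plan says.** **Hypothesis.** Section 11.1 states that, relative to standard care, "these patients will have higher levels of satisfaction with their overall experience". Section 1.2 says the same. The null in 11.1 refers only to satisfaction, compared with standard-care patients.

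**Objective and endpoint.** Section 2.1.2 words the objective as "To assess patient satisfaction with their procedure" and adds: "This will be assessed through a patient satisfaction survey including Likert-type questions". Section 2.2.2 says the endpoint "is the response to Questions 18 of the post-procedure survey". Section 11.2 lists it as "Q18, which is on a 5-level Likert scale, measuring satisfaction", measured only after the procedure, and gives it a two-sided test for ordinal data without naming the test. Section 6.3 lists the instrument in the plural: "Patient satisfaction questions".

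**Instrument.** The Q18 stem in Appendix B reads "Please rate your satisfaction with each of the following parts of your bone marrow biopsy experience". Three rows follow, each on five levels: the time spent in the room beforehand, contact with staff, and the decor. Q22 asks for overall satisfaction, but in relation to the intervention. The notes and display logic in Appendix B show Q19 to Q23 only to patients outside the control group. Q22 is not a listed endpoint.

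**The concern.** The hypothesis compares overall satisfaction between arms, so it needs an overall rating from both arms. The survey collects one only from intervention patients. The designated endpoint covers three parts of the visit. None asks about the VR session or the biopsy, and one rates the decor, which Intervention 2 itself changes. A better decor score in Phase II is a relevant finding, but it would not by itself show a better overall experience.

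A second gap concerns the analysis. Section 11.2 treats Q18 as one variable, whereas the survey delivers three. If the rows are tested one by one, there is no multiplicity rule and no key row. If they are combined, no summary is named. Section 15.3 plans a preliminary report after Phase I, so a rule not fixed by then would be chosen with Phase I results known.

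**Working it through.** **The plan's own figure.** No power or effect size is given for satisfaction. The only power statement (11.3) concerns distress: 15 per arm, effect size 1.1, two-sided 5% t-test. With 28 degrees of freedom and noncentrality 1.1 × √(15/2) = 3.01, power is 82.84%, against the stated 82.8%. It reproduces and is not affected by this point.

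**Who gives an overall rating** (arm sizes from 3.2 and 11.3, display logic from Appendix B):

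| Item | Rates the overall experience? | Intervention (15 + 15 = 30) | Control (15 + 15 = 30) |
|---|---|---|---|
| Q18, three rows | No (0 of 3 rows) | asked | asked |
| Q22 | Yes, in relation to the intervention | asked | not asked |
| Q24 | Free text, not a rating | asked | asked |

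Controls therefore supply 0 of 30 overall ratings, and a between-arm comparison of overall satisfaction does not exist in the data.

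**False-positive risk if each row is tested at 5%** (an assumption, since the plan does not say):

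- Three independent tests in one phase: 1 − 0.95³ = 0.143.
- Six independent tests over both phases: 1 − 0.95⁶ = 0.265.
- Correlated rows, by simulation: 15 per arm, three 5-level rows cut from correlated normal variables, rank-sum test with continuity correction, 6,000 trials per scenario. Control distributions were assumed to be 3/7/20/40/30% and 5/15/40/30/10%. The chance of at least one false positive was 11.7–12.5% at correlation 0.3–0.5, 10.2–11.7% at 0.7, and 9.0–9.1% at 0.9.
- A separate simulation used another assumed distribution (5/10/20/35/30%), no continuity correction and 4,000 trials. It gave 13.1% at 0.3, 12.9% at 0.5 and 10.8% at 0.8.

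Taken together, the range is about 9–13%.

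**How much the unstated choice matters (illustration only).** The assumed shift is 1.1 latent standard deviations, borrowed from the distress calculation, with correlations 0.3–0.7 and the first set of simulation settings above. Testing one shifted row has 69–77% power at 5%, or 50–59% at 0.05/3 = 1.67%. For a summary of the three rows:

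| Rows that shift | Power of the sum | Power of the median |
|---|---|---|
| One | 12–21% | 10–15% |
| Two (wait and decor) | 41–68% | 54–66% |
| Three | 84–96% | 78–92% |

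A summary dilutes an effect confined to one part and gains power when all parts improve. Neither approach is better in general, so the choice has to be made in advance.

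**The case against.** The best defence is that Q18 is the chosen operational definition. The objective in 2.1.2 speaks of satisfaction with the procedure, 2.2.2 defines it as Q18, and both arms answer Q18, so a randomized satisfaction comparison does exist. On this reading the phrase about overall experience in 1.2 and 11.1 is loose wording, and rewording the hypothesis would close the gap. It is right that Q18 is a partial measure and not an invalid one, and that rewording would remove the mismatch. But the protocol summary itself gives overall patient experience as the reason for assessing satisfaction, and 1.1 sets improving it as the goal of the study. Rewording alone would leave that aim unmeasured in controls.

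On the analysis, the five-level description fits a single row, whereas a sum of three rows runs from 3 to 15 and has 13 levels. One ordinal test per row is therefore the more natural reading. That narrows the gap to the missing multiplicity rule or key row. Unadjusted secondary tests in a small trial would be a modest fault if reported as such, and this part would not carry the point alone.

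The power figures rest on an assumed shift, assumed distributions and assumed correlations. The main conclusion does not depend on them.

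**Conclusion.** The concern holds. The hypothesis of higher overall satisfaction than under standard care cannot be tested directly. This follows from the display logic and the text of Q18 alone, with no statistical assumption. It can only be approached through three parts of the visit.

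The unspecified handling of the three rows is a lesser fault. The 14.3% figure assumes row-wise testing and independence, and the 9–13% range assumes row-wise testing and the stated correlations and distributions. The endpoint is secondary and has no power claim, so the change is one that should be made, but the omission does not threaten the main result.

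**What to change.** Add one row to Q18, shown to every participant on the same five-point scale and worded without reference to arm, for example: *Your overall bone marrow biopsy experience today*. Name this row as the satisfaction endpoint in 2.2.2 and 11.2. Compare Intervention with Control within each phase by a two-sided Wilcoxon rank-sum test or a proportional-odds model; this also settles the loosely worded Q18 contrast in 11.2. Report the three existing rows and Q22 as supportive or descriptive. The reason for this choice is that the new row measures the stated hypothesis, not that it has more power: a sum would have more if all three parts improved.

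If enrolment has begun, introduce the row preferably at the start of a phase, analyse it only in those asked, and report how many were asked per arm. For a completed phase, or if the survey cannot be changed, specify before looking at the data either one summary of the three rows or row-wise tests with an adjustment such as Holm. In that case, restate the hypothesis as satisfaction with those parts of the visit.

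The cost is a few seconds per patient and an IRB-approved amendment of Appendix B, 2.2.2 and 11.2 (required by 14.2 and the Appendices page), with no extra patients, visits or staff. The drawback of a mid-study change is that patients already surveyed lack the item. If it starts with Phase II, 30 of 60 patients (15 against 15) have it and only Intervention 2 gets an overall comparison. That comparison stays randomized, because 3.4.1 provides for block randomization in each phase.

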| Précis: | Patients undergoing a bone marrow biopsy aspiration (BMBA) will trial possible interventions to decrease their distress and pain , as suggested by a previous patient survey conducted with this population. The study will assess both pre-intervention and post-intervention distress scores and a post-intervention pain score. Patient satisfaction will also be assessed to determine overall patient experience. Each intervention will be compared to a control group to validate if one or both interventions are valuable to offer to patients in the future. |
| Objectives: | 
Primary: Trial VR and environmental interventions to determine if either result in a reduction in patient distress during BMBA.
 
Secondary: Determine if either intervention results in decreased pain or improved satisfaction scores.
 |
| Population: | 
Young adult to geriatric patients with hematologic malignancies of varying health statuses and demographic groups
 
Most patients have hematological cancers, including leukemia, lymphoma, and multiple myeloma.
 |
| Phase: | N/A |
| Number of Sites: | TJU |
| Description of Intervention: | 
Two interventions will be trialed. The first intervention is virtual reality (VR) guided mediation. Patients will be provided with wireless VR headsets that contain a guided meditation application. The application allows users to select their preferred music, visual setting, and a topic for meditation.
 
The second intervention is environmental changes. A nature themed wall mural decal will be installed in the BMBA room and the in-room computer will play music from Pandora. A selection of suggested stations will be provided, with the option for outside selections.
 |
| Study Duration: | 10 months |

| | |
|---|--|
| Participant Participation Duration: | Approximately 45 minutes, the duration of a normal BMBA visit, including procedure |
| Estimated Time to Complete Enrollment: | 6 months |

Schematic of Study Design:

1 Introduction

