2.2 Endpoints/Outcome Measures

Primary outcomes will be assessed via the patient questionnaires. All endpoints are measured pre- and post-procedure at Visit 1.

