4.1 Eligibility Criteria

4.1.1 Inclusion Criteria

Individuals must meet all of the following inclusion criteria in order to be eligible to participate in the study:

- Provide signed and dated informed consent form
- Willing to comply with all study procedures
- Over 18 years of age
- Prior history of at least 1 (one) BMBA at Jefferson outpatient oncology office within the past 2 (two) years
- Visiting the Jefferson outpatient oncology office for a BMBA procedure during the study duration

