- Bone or Muscle conditions (for example osteoporosis, arthritis)
- Heart or Cardiovascular conditions (for example heart attack, heart disease)
- Inflammation and immune conditions (for example Rheumatoid arthritis)
- Kidney or Renal conditions (for example kidney disease)
- Lung or Pulmonary conditions (for example asthma, COPD)
- Mental health (for example anxiety, depression)
- Nutrition, Exercise or Metabolic conditions (for example diabetes, obesity)
- Stomach or Gastrointestinal conditions (for example Crohn's disease)
- Other (*please include if not listed*)

- Prefer not to answer

End of Block: Background Health

Start of Block: BMBA History

Please answer the following questions about your previous bone marrow biopsy visits.

Q10 When was your **most recent** bone marrow biopsy at Jefferson Health?

- Less than one month ago
- One to five months ago
- Six months to one year ago
- Greater than one year ago

Q11 How many bone marrow biopsies have you had in the past **two years**?

- One
- Two or three
- Four or five
- Six or more

Q12 During your last bone marrow biopsy procedure experience, how would you rate your **pain**, on a scale of 0 to 10, with 0 being *no pain* and 10 being *extreme pain*?

- 0
- 1
- 2
- 3
- 4
- 5
- 6
- 7
- 8
- 9
- 10

End of Block: BMBA History

Start of Block: Distress Assessment

The following questions are about the **distress** you may feel about today's procedure.

Distress is an unpleasant experience of a mental, physical, social, or spiritual nature. It can affect the way you think, feel, or act. Distress may make it harder to cope with having cancer, its symptoms, or its treatment.

Q13 On a scale of 0 to 10, with 0 being *no distress* and 10 being *extreme distress*, how much **distress** do you feel today?

0

1

2

3

4

5

6

7

8

9

10

Q14 What part(s) of a bone marrow biopsy procedure make you feel **distressed**? (Select all that apply).

- Being in a medical setting
- Sitting and waiting before the provider comes in
- Thinking about the pain I might feel
- Worrying about the process of the procedure
- Worrying about the results of the procedure
- None of the above, I don't feel distress about bone marrow biopsies.
- Other: _____

Q15 How do you **deal with feeling distressed** about bone marrow biopsies? (Select all that apply.)

- I bring a friend or relative with me to my appointments
- I distract myself with my phone, a book, or a magazine
- I listen to music

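### Distress and pain are tested as unadjusted post-minus-pre differences, and for pain the value subtracted is recall of an earlier biopsy, not a pre-procedure score

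*Combined protocol and SAP*

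**What the plan says.** Section 11.2: "The numeric difference between post vs. pre responses of Q13, Q16, Q12 and Q17 will be compared" between each intervention and its own phase control by two-sample t-test. No covariate is named anywhere. Section 11.3 powers the same distress difference: 15 per arm, effect size 1.1, two-sided 5%, 82.8%.

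The two differences are of different kinds. Q13 asks about distress today and Q16 about distress after the procedure. For pain, Q12 sits in the survey's biopsy-history block and reads "During your last bone marrow biopsy procedure experience, how would you rate your pain"; Q17 asks about today's biopsy. Eligibility (4.1.1) requires "Prior history of at least 1 (one) BMBA at Jefferson outpatient oncology office within the past 2 (two) years".

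The descriptions of pain do not agree with each other or with the survey:
- Section 2.2: "All endpoints are measured pre- and post-procedure at Visit 1". Section 11.2 repeats "All endpoints are measured pre- and post-procedure".
- Section 1.2: "This study aims to evaluate pre-procedure and post-procedure distress and" pain scores.
- Section 2.2.2: the pain endpoints "are the responses to Question 12 and 17 of the post-procedure survey", although Q12 comes before the survey's divider.
- Synopsis: "pre-intervention and post-intervention distress scores and a post-intervention pain score".
- Section 6.2 lists no pain item in the pre-procedure survey.

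Section 6.2 lists randomisation before the pre-procedure survey. Appendix B has staff enter the arm (Q2) at randomisation, before the patient starts the survey.

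**The concern.** A change score fixes the coefficient on the baseline at 1. A regression estimates it. With 15 per arm, a poorly chosen coefficient can cost as much power as several patients per arm.

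For pain the problem goes beyond efficiency. The value subtracted belongs to a different procedure, recalled later. A weak correlation with today's pain is plausible, and subtracting a weakly correlated score adds noise. A reader told that all endpoints are pre- and post-procedure measures would also take Q17 minus Q12 for a change during this visit.

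Both the difference and an adjusted model need baseline answers unaffected by allocation. With the envelope opened before the survey, that is not guaranteed.

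**Working it through.** **Inputs.** From 11.3: 15 per arm, effect size 1.1 (read as SDs of the post-minus-pre difference), two-sided 5%. The documents give no SD and no correlation. So rho (pre-post correlation), k (SD pre / SD post) and any pain effect size are assumptions, shown over a range.

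**1. The plan's own figure.** Noncentrality 1.1 × √(15/2) = 3.01, df 28: power 82.84%. The 82.8% reproduces.

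**2. Variances, in units of the post-score variance.**
- Change score: 1 + k² − 2·rho·k
- Adjusted for baseline: 1 − rho²
- Post score alone: 1

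Change minus adjusted is (k − rho)², so the adjusted residual variance is never larger. The two are equal only when the post-on-pre slope rho/k is 1. With k = 1 the ratio of adjusted to change is (1 + rho)/2. The change score is worse than ignoring the baseline when rho < k/2. Adjustment costs one degree of freedom (27) and slope estimation (information factor 26/27).

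**3. Distress.** The true effect is held at 1.1 change-score SDs, so the planned test always has 82.8%. Adjusted noncentrality = 1.1 × √[(1 + k² − 2·rho·k)/(1 − rho²)] × √(7.5 × 26/27).

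| rho | k = 0.8 | k = 1 | k = 1.25 |
|---|---|---|---|
| 0.3 | 89.6% | 94.2% | 98.0% |
| 0.5 | 85.4% | 90.8% | 96.5% |
| 0.7 | 82.1% | 87.1% | 94.9% |
| 0.8 | 81.3% | 85.2% | 94.5% |
| 0.9 | 83.2% | 83.2% | 95.5% |

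At k = 1 these rows are raw effects of 1.30, 1.10, 0.85, 0.70 and 0.49 post-score SDs. Also at k = 1, the gain vanishes at rho 0.92, and rho 0.95 gives 82.3%. When the slope is exactly 1, noncentrality is 1.1 × √(7.5 × 26/27) = 2.96 and power is 81.3%. This is the floor, 1.5 points below plan. The t-test needs 19 per arm (91.0%) to match 90.8%, and 16 per arm (85.3%) to match 85.2%.

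Simulation with normal scores (k = 1, 40,000 runs per setting) gave adjusted power of 94.3%, 90.8%, 86.8%, 85.5% and 83.3% at the same five correlations. With scores rounded and clipped to 0–10 (assumed mean 5.5, SD 2.5), adjusted against unadjusted was 93.4% v 80.5%, 89.7% v 80.2%, 85.2% v 79.7%, 81.9% v 78.8% and 77.3% v 76.3%. The adjusted test rejected a true null in 4.95% to 5.02% of runs.

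**4. Pain.** The effect is assumed to be 1.1 SD of Q17. Planned noncentrality = 1.1 × √7.5 / √(1 + k² − 2·rho·k).

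| rho | Difference, k = 0.8 | k = 1 | k = 1.25 | Q17 alone | Adjusted, any k |
|---|---|---|---|---|---|
| 0 | 62.2% | 53.9% | 44.3% | 82.8% | 81.3% |
| 0.2 | 71.6% | 63.3% | 52.6% | 82.8% | 82.9% |
| 0.3 | 77.0% | 69.1% | 57.9% | 82.8% | 84.8% |
| 0.6 | 94.1% | 90.2% | 80.5% | 82.8% | 94.5% |

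The planned difference ranges from poor to good with rho and k. The adjusted analysis is at or near the best column in every row.

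**5. Order of events.** Section 6.2 runs consent, eligibility check, envelope, survey. Appendix B hides the arm field from the patient by removing the back button, but nothing says that staff withhold the allocation until Q12 and Q13 are answered.

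**The case against.** The strongest reply is that the distress analysis is not an error. It is valid under randomisation and 11.3 powers exactly that test. The gain depends on inputs the documents do not give. At k = 0.8 and rho 0.7 to 0.8 adjustment loses slightly, and showing the patient's Q13 answer inside Q16 may push rho up. At k = 1 and rho 0.8 the gain is worth one patient per arm, not several. All of this stands. It limits how large a benefit can be promised, but the possible loss remains capped at about 1.5 points while the possible gain is much larger.

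For pain, the same patient rates the same type of procedure twice, so rho could exceed 0.3. At rho 0.6 the difference beats Q17 alone when k is 0.8 or 1. That also stands, but adjustment still does slightly better there (94.5% against 94.1% and 90.2%) and does not require guessing rho. Pain is a secondary endpoint with no claimed power, and 11.2's own list does not call Q12 pre-procedure. But the general statements in 2.2 and 11.2, and the aim in 1.2, do cover it.

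On survey order, the missing back button and the arm-specific instructions coming after the survey are partial safeguards. They do not stop a patient learning the arm from staff once the envelope is open. What is needed is a baseline unaffected by allocation; completing the items first is the simplest way to secure it.

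Finally, 82.8% would refer to a test no longer used for inference. It can stand as the unadjusted reference if labelled so.

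**Conclusion.** The concern holds, as a change that should be made rather than a flaw that invalidates the trial. The 82.8% is correct and the distress t-test is valid, provided Q13 is unaffected by allocation.

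- **Distress:** at equal SDs, adjustment takes power from 82.8% to between 94.2% (rho 0.3) and 82.3% (rho 0.95). Over any rho and k it cannot fall below 81.3%. The size of the gain is uncertain; the bound on the loss is not.
- **Pain:** the mislabelling needs no assumption. Q12 is recall of an earlier biopsy, and the wording in 1.2, 2.2, 2.2.2 and 11.2 is wrong for it. The power loss from subtraction is conditional. It occurs relative to Q17 alone when rho < k/2, and at k = 1 and rho 0 to 0.3 it is about 14 to 29 points (82.8 − 69.1 and 82.8 − 53.9), for an assumed effect of 1.1 SD.
- **Order:** as written, Q12 and Q13 are not guaranteed to be answered before allocation.

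**What to change.** - **11.2:** within each phase, fit a linear model of Q16 on arm with Q13 as covariate, and of Q17 on arm with Q12 as covariate. Test at two-sided 5% and report the adjusted mean difference with 95% CI. Report change scores descriptively only.
- **1.2, 2.2, 2.2.2, 11.2:** label Q12 as recalled pain at the last BMBA, stop describing pain as a pre/post measure, and place Q12 in the pre-procedure part of the survey.
- **6.2 and Appendix B:** have the patient complete the pre-procedure survey, including Q12 and Q13, before the envelope is opened. Move staff entry of Q2 to the divider block. This works because no item depends on the arm until after Q18.
- **11.3:** keep 82.8% as the unadjusted basis, and state the rho and SD ratio assumed for any adjusted power.

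**Cost.** Wording in six sections plus Appendix B, one reordered step and one model line. The protocol treats appendix changes as amendments, and 14.2 requires IRB approval of any amendment before it takes effect. No new data and no added patients. The statistical price is at most about 1.5 power points for the distress effect, when the post-on-pre slope is near 1.
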